4.6.3 Study Discontinuation

The Sponsor has the right to terminate this study at any time. Reasons for terminating the study may include, but are not limited to, the following:

- The incidence or severity of adverse events in this or other studies indicates a potential health hazard to patients
- Patient enrollment is unsatisfactory

The Sponsor will notify the investigator if the Sponsor decides to discontinue the study.

4.6.4 Site Discontinuation

The Sponsor has the right to close a site at any time. Reasons for closing a site may include, but are not limited to, the following:

- Excessively slow recruitment
- Poor protocol adherence
- Inaccurate or incomplete data recording
- Non-compliance with the ICH guideline for Good Clinical Practice
- No study activity (i.e., all patients have completed the study and all obligations have been fulfilled)

5. ASSESSMENT OF SAFETY

5.1 SAFETY PLAN

AT-527 is not approved, and clinical development is ongoing. The safety plan for patients in this study is based on clinical experience with AT-527 completed and ongoing studies. The anticipated important safety risks for AT-527 are outlined below. Please

refer to the AT-527 Investigator's Brochure for a complete summary of safety information.

Several measures will be taken to ensure the safety of patients participating in this study. Eligibility criteria have been designed to exclude patients at higher risk for toxicities. Throughout the duration of the study, patients will undergo safety monitoring including assessment of the nature, frequency, and severity of adverse events.

5.1.1 Risks Associated with AT-527

AT-527 has been evaluated in two completed clinical studies (AT-01B-001 and AT-01B-002) in healthy volunteers and HCV-infected patients. In the first study, 88 subjects were dosed with blinded study drug (AT-527 or placebo), with 72 of the 88 subjects receiving active study drug. AT-527 was well-tolerated in both healthy volunteers and HCV-infected patients as either single or multiple doses (seven daily doses) up to 600 mg of AT-527 (equivalent to 553 mg AT-511 free base). In the second study, 10 HCV-infected patients received AT-527 550 mg in combination with 60 mg daclatasvir QD for 8-12 weeks. There were no serious adverse events, dose-limiting toxicities, or premature discontinuations.

In the COVID-19 development program, AT-527 is being evaluated in one Phase I study (AT-03A-002) in healthy volunteers and two Phase II studies in COVID-19 patients (AT-03A-001 and WV43042). In the ongoing study AT-03A-002, the completed Cohorts 1 and 3 investigated AT-527 doses at 550 mg (as 1 × 550 mg tablet) or placebo BID for 5 days and 825 mg (as 3 × 275 mg) or placebo BID for 10 days, respectively. The completed Cohort 2 investigated a single dose of 550 mg (as 2 × 275 mg tablets). Preliminary safety data from 41 subjects in the completed Cohorts 1–3 show no premature discontinuations due to AT-527-related AEs, no SAEs, and no patterns with regards to laboratory-, ECG-, or vital sign abnormalities. In the ongoing study AT-03A-001, AT-527 is being evaluated at a dose of 550 mg BID in hospitalized patients with moderate COVID-19 and risk factors for poor outcomes. Preliminary results from an interim analysis performed after the first 70 patients show that AT-527 was generally well tolerated. There were no drug-related SAEs. Non-serious AEs were equally distributed across treatment arms. Most were mild-to-moderate in severity and assessed as not related to the study drug. No safety concerns or newly determined risks were identified. (see further detail in Section 1.2 and 1.3).

In the current study (WV43042), a planned interim safety analysis after the first 30 patients enrolled in Cohort A (dosed at 550 mg BID for 5 days) had completed assessments through Day 10, identified no safety concerns. All AEs were Grade 1 or 2 in severity and no SAEs were reported.

Some nucleoside analogs have been associated with mitochondrial toxicity, resulting in damage to liver, muscles, heart, nerve, pancreas, and other organs. Nephrotoxicity has also been associated with the use of some nucleoside analogs (e.g., tenofovir) but is not a broad class effect. The completed nonclinical assessments suggested no potential for mitochondrial toxicity with AT-527. To date, there have been no clinical signs of adverse events suggesting mitochondrial toxicity for AT-527 dosing.

To date, there have been no appreciable patterns of treatment-related or dose-related clinical adverse events or laboratory abnormalities from nonclinical or clinical studies.

5.1.2 Management of Patients Who Experience Adverse Events

5.1.2.1 Dose Modifications

There will be no dose modifications for study drug in this study.

5.1.2.2 Treatment Interruption

Treatment interruptions will not be permitted for study drug in this study.

5.1.2.3 Management of Increases in QT Interval

Study drug should be discontinued in patients who develop any of the following, unless there is a clear alternative cause for the changes:

- Sustained (at least two ECG measurements >30 minutes apart) QTcF that is >500 ms and >60 ms longer than the baseline value
- An episode of torsades de pointes or a new ECG finding of clinical concern

Management of patients with sustained QTcF prolongation should include close monitoring, with ECGs repeated at least hourly until two successive ECGs show resolution of the findings, correction of any electrolyte abnormalities, and possible discontinuation of other concomitant medications that are known to prolong the QT interval. Consultation with a cardiologist or electrophysiologist is recommended, to help in the management of such patients.

5.2 SAFETY PARAMETERS AND DEFINITIONS

Safety assessments will consist of monitoring and recording adverse events, including serious adverse events and adverse events of special interest, performing protocol-specified safety laboratory assessments, measuring protocol-specified vital signs, and conducting other protocol-specified tests that are deemed critical to the safety evaluation of the study.

Certain types of events require immediate reporting to the Sponsor, as outlined in Section 5.4.

5.2.1 Adverse Events

According to the ICH guideline for Good Clinical Practice, an adverse event is any untoward medical occurrence in a clinical investigation subject administered a

pharmaceutical product, regardless of causal attribution. An adverse event can therefore be any of the following:

- Any unfavorable and unintended sign (including an abnormal laboratory finding), symptom, or disease temporally associated with the use of a medicinal product, whether or not considered related to the medicinal product
- Any new disease or exacerbation of an existing disease (a worsening in the character, frequency, or severity of a known condition) (see Sections [5.3.5.9](#) and [5.3.5.10](#) for more information)
- Recurrence of an intermittent medical condition (e.g., headache) not present at baseline
- Any deterioration in a laboratory value or other clinical test (e.g., ECG, X-ray) that is associated with symptoms or leads to a change in study treatment or concomitant treatment or discontinuation from study drug
- Adverse events that are related to a protocol-mandated intervention, including those that occur prior to assignment of study treatment (e.g., screening invasive procedures such as biopsies)

5.2.2 Serious Adverse Events (Immediately Reportable to the Sponsor)

A serious adverse event is any adverse event that meets any of the following criteria:

- Is fatal (i.e., the adverse event actually causes or leads to death)
- Is life-threatening (i.e., the adverse event, in the view of the investigator, places the patient at immediate risk of death)

This does not include any adverse event that, had it occurred in a more severe form or was allowed to continue, might have caused death.

- Requires or prolongs inpatient hospitalization (see Section [5.3.5.11](#))
- Results in persistent or significant disability/incapacity (i.e., the adverse event results in substantial disruption of the patient's ability to conduct normal life functions)
- Is a congenital anomaly/birth defect in a neonate/infant born to a mother exposed to study drug
- Is a significant medical event in the investigator's judgment (e.g., may jeopardize the patient or may require medical/surgical intervention to prevent one of the outcomes listed above)

The terms "severe" and "serious" are not synonymous. Severity refers to the intensity of an adverse event (e.g., rated as mild, moderate, or severe, or according to NCI CTCAE; see Section [5.3.3](#)); the event itself may be of relatively minor medical significance (such as severe headache without any further findings).

Severity and seriousness need to be independently assessed for each adverse event recorded on the eCRF.

Serious adverse events are required to be reported by the investigator to the Sponsor immediately (i.e., no more than 24 hours after learning of the event; see Section 5.4.2 for reporting instructions).

5.2.3 Adverse Events of Special Interest (Immediately Reportable to the Sponsor)

Adverse events of special interest are required to be reported by the investigator to the Sponsor immediately (i.e., no more than 24 hours after learning of the event; see Section 5.4.2 for reporting instructions). Adverse events of special interest for this study are as follows:

- Cases of potential drug-induced liver injury that include an elevated ALT or AST in combination with either an elevated bilirubin or clinical jaundice, as defined by Hy's Law (see Section 5.3.5.6)
- Suspected transmission of an infectious agent by the study drug, as defined below
Any organism, virus, or infectious particle (e.g., prion protein transmitting transmissible spongiform encephalopathy), pathogenic or non-pathogenic, is considered an infectious agent. A transmission of an infectious agent may be suspected from clinical symptoms or laboratory findings that indicate an infection in a patient exposed to a medicinal product. This term applies only when a contamination of the study drug is suspected.

5.3 METHODS AND TIMING FOR CAPTURING AND ASSESSING SAFETY PARAMETERS

The investigator is responsible for ensuring that all adverse events (see Section 5.2.1 for definition) are recorded on the Adverse Event eCRF and reported to the Sponsor in accordance with instructions provided in this section and in Sections 5.4–5.6.

For each adverse event recorded on the Adverse Event eCRF, the investigator will make an assessment of seriousness (see Section 5.2.2 for seriousness criteria), severity (see Section 5.3.3), and causality (see Section 5.3.4).

5.3.1 Adverse Event Reporting Period

Investigators will seek information on adverse events at each patient contact. All adverse events, whether reported by the patient or noted by study personnel, will be recorded in the patient's medical record and on the Adverse Event eCRF.

After informed consent has been obtained but prior to initiation of study drug, only serious adverse events caused by a protocol-mandated intervention (e.g., invasive procedures such as biopsies, discontinuation of medications) should be reported (see Section 5.4.2 for instructions for reporting serious adverse events).

After initiation of study drug, all adverse events will be reported until 28 days after the final dose of study drug.

Instructions for reporting adverse events that occur after the adverse event reporting period are provided in Section 5.6.

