4.3.2 Study Treatment Dosage, Administration, and Compliance

The treatment regimens are summarized in Section 3.1.

Patients in Cohort A will self-administer AT-527 (or placebo) tablets at a dose of 550 mg orally BID on Days 1–5. AT-527 (or placebo) tablets should be taken approximately 12 hours apart. If the first dose is taken after 4 p.m. (16:00 hours) on Day 1, the next dose will be taken the morning of Day 2. For these patients, the tenth dose will be taken on the morning of Day 6. If the first dose is taken prior to 4 p.m. (16:00 hours) on Day 1, the next dose should be taken in the evening of the same day (i.e., prior to midnight on the same calendar day with a minimum of 8 hours between doses). For these patients, the tenth dose will be taken in the evening of Day 5. AT-527 (or placebo) may be taken with or without a meal. AT-527 (or placebo) tablets should be swallowed whole with a glass of water and should not be chewed, cut, or crushed. If a dose of AT-527 (or placebo) is missed (i.e., not taken within 12 hours after the scheduled dosing time), the patient should resume dosing with the next scheduled dose. If a patient vomits after taking a dose, a replacement tablet should not be taken, dosing should resume with the next scheduled dose. To assess patient compliance with self-administration of AT-527 (or placebo), patients will be required to record the time and date they took each dose in a medication diary; missed doses will also be recorded. Patients will be instructed to bring their bottles of AT-527 (or placebo) and their medication diaries to each study visit.

If a BID regimen is selected for Cohorts B–E, patients will follow the dose administration guidance described above for Cohort A. For other dose regimens, refer to the pharmacy manual for detailed instructions on drug preparation and administration.

Details on treatment administration (e.g., dose and timing) should be noted on the Study Drug Administration electronic Case Report Form (eCRF). Cases of overdose or medication error, along with any associated adverse events, should be reported as described in Section 5.3.5.11.

Guidelines for dosage modification and treatment interruption or discontinuation for patients who experience adverse events are provided in Section 5.1.2.

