5.4.2.2 Events That Occur after Study Drug Initiation

After initiation of study drug, serious adverse events and adverse events of special interest will be reported until 28 days after the final dose of study drug. Investigators should record all case details that can be gathered immediately (i.e., within 24 hours after learning of the event) on the Adverse Event eCRF and submit the report via the electronic data capture (EDC) system. A report will be generated and sent to Roche Safety Risk Management by the EDC system.

In the event that the EDC system is unavailable, the paper Clinical Trial Serious Adverse Event/Adverse Event of Special Interest Reporting Form provided to investigators should be completed and submitted to the Sponsor or its designee immediately (i.e., no more than 24 hours after learning of the event), either by faxing or by scanning and emailing the form using the fax number or email address provided to investigators. Once the EDC system is available, all information will need to be entered and submitted via the EDC system.

Instructions for reporting serious adverse events that occur > 28 days after the final dose of study treatment are provided in Section [5.6](#).

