5.6 ADVERSE EVENTS THAT OCCUR AFTER THE ADVERSE EVENT REPORTING PERIOD

The Sponsor should be notified if the investigator becomes aware of any serious adverse event that occurs after the end of the adverse event reporting period (defined as 28 days after the final dose of study drug), if the event is believed to be related to prior exposure to study drug. These events should be reported through use of the Adverse Event eCRF. However, if the EDC system is not available, the investigator should report these events directly to the Sponsor or its designee, either by faxing or by scanning and emailing the paper Clinical Trial Serious Adverse Event/Adverse Event of Special Interest Reporting Form using the fax number or email address provided to investigators.

5.7 EXPEDITED REPORTING TO HEALTH AUTHORITIES, INVESTIGATORS, INSTITUTIONAL REVIEW BOARDS, AND ETHICS COMMITTEES

The Sponsor will promptly evaluate all serious adverse events and adverse events of special interest against cumulative product experience to identify and expeditiously communicate possible new safety findings to investigators, IRBs, ECs, and applicable health authorities based on applicable legislation.

To determine reporting requirements for single adverse event cases, the Sponsor will assess the expectedness of these events through use of the reference safety information in the document listed below:

Drug	Document
AT-527	AT-527 Investigator's Brochure

The Sponsor will compare the severity of each event and the cumulative event frequency reported for the study with the severity and frequency reported in the applicable reference document.

Reporting requirements will also be based on the investigator's assessment of causality and seriousness, with allowance for upgrading by the Sponsor as needed.

An aggregate report of any clinically relevant imbalances that do not favor the test product will be submitted to health authorities.

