Appendix 3: Schedule of Activities for Cohort E

- ⁿ All women of childbearing potential will have a pregnancy test (urine or serum) at screening.
- ^o Nasopharyngeal swab samples should be collected at screening and once per day on Days 1, 3, 5, and 7. Swab samples should be collected from both nostrils at all timepoints. Screening samples will be used for point-of-care RT-PCR or rapid antigen testing to determine eligibility.
- ^p Sample must be collected prior to dosing.
- ^q Samples for PBMC may not be collected at some timepoints if sample stability requirements for processing will not be met. Please refer to the laboratory manual for more detail. A plasma sample will be generated from the blood sample obtained following PBMC processing and will be stored for biomarker research. No additional blood draw is needed.
- ^r Collection of blood sample for RNA analysis using PAXgene tubes.
- ^s Not applicable for a site that has not been granted approval for WGS. If the sample is not collected on Day 1 for any reason, it may be collected at any later timepoint.
- ^t Randomization will be performed as soon as possible after screening and within 72 hours.
- ^u First dose on Day 1 must be administered as soon as possible after randomization and within 24 hours. For BID regimens, AT-527 (or placebo), should be taken approximately 12 hours apart. If the first dose is taken after 4 pm (16:00 hours) on Day 1, the next dose will be taken in the morning of Day 2. For these patients, the 10th dose will be taken on the morning of Day 6. If the first dose is taken prior to 4 pm (16:00 hours) on Day 1, the next dose should be taken in the evening of the same day (i.e., prior to midnight on the same calendar day with a minimum of 8 hours between doses). For these patients, the 10th dose will be taken in the evening of Day 5. For other dose regimens see Pharmacy manual for details of dosing instruction.
- ^v Medication (e.g., prescription drugs, over-the-counter drugs, vaccines, herbal or homeopathic remedies, nutritional supplements) used by a patient in addition to protocol-mandated treatment from 7 days (12 months for COVID-19 vaccines) prior to initiation of study drug until the end of study follow-up telephone call on Day 33.

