- ^w After informed consent has been obtained but prior to initiation of study drug, only serious adverse events caused by a protocol-mandated intervention should be reported. After initiation of study drug, all adverse events will be reported until the end of study follow-up telephone call on Day 33.

Appendix 4

Schedule of Pharmacokinetic Samples

	Cohort A	Cohorts B–E		
	BID Regimen	BID Regimen	TID Regimen	QD Regimen
Day 1	Predose ^{a, c}	Predose ^{a, c}	Predose ^{a, c}	Predose ^{a, c}
	1 and 3 hours postdose ^{b, c}	1 and 4 hours postdose ^{b, c}	1 hour postdose ^{b, c} Predose [with reference to second dose of the day] ^{a, c}	1 and 4 hours postdose ^{b, c}
Day 3	Predose ^{a, c}	Predose ^{a, c}	Predose ^{a, c}	Predose ^{a, c}
Day 5	Predose ^{a, c} and 3 hours postdose ^{b, c}	Predose ^{a, c}	Predose ^{a, c}	Predose ^{a, c}
		1 and 4 hours postdose ^{b, c} Predose [with reference to second dose of the day] ^{a, c}	1 hour postdose ^{b, c}	1 and 4 hours postdose ^{b, c}
Day 7	48 (\pm 1) hours ^{c, e}	Anytime ^{c, d}	Anytime ^{c, d}	Anytime ^{c, d}
Early termination	—	Sample to be collected if early termination occurs on or before Day 7		

BID = twice a day; QD = once a day; TID = three times a day.

Note: Unless otherwise specified (TID regimen), all timepoints are in relation to the first dose administered on a given day.

^a Predose sampling window: within 30 minutes prior to dose administration.

^b Postdose sampling window: \pm 30 minutes from scheduled sampling time.

^c For patients at participating sites who have provided written or electronic informed consent to participate in mobile nursing visits, this assessment or procedure may be performed by a trained nursing professional at the patient's home.

^d The exact sampling time will be captured in relation to the time of last (10th) dose.

^e In Cohort A, the 48-hour PK sampling on Day 7 is with reference to the first dose on Day 5.

Appendix 5
COVID-19 Symptom Diary
and Patient Global Impression of Severity

Do not reproduce or distribute. The Sponsor will provide sites with all instruments to be completed in this study.

Note that the following is a sample. Sites will be provided with separate versions of the diary for Days 1–14 (morning vs. evening, including recording of temperature) and Days 15–28 (evening, including recording of temperature).

Today's date: _____ Time completing: _____

COVID-19 Evening Symptom Diary

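### The closing safety call may fall up to 4 days before the stated 28-day adverse event reporting period ends, and the appendices end reporting at that call

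*Protocol*

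**What the plan says.** Three sections of the protocol body tie the end of reporting to the patient's own last dose. Section 5.3.1 covers all adverse events: "all adverse events will be reported until 28 days after the final dose of study drug". Section 5.4.2.2 sets the same limit for the events that need immediate reporting: "serious adverse events and adverse events of special interest will be reported until 28 days after the final dose of study drug". Section 5.6 repeats it when it describes what happens after the period closes: "defined as 28 days after the final dose of study drug".

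The schedules use a different end point. The adverse event footnote of Appendix 3 (Cohort E) reads "all adverse events will be reported until the end of study follow-up telephone call on Day 33", and the matching footnotes of Appendix 1 (Cohort A) and Appendix 2 (Cohorts B–D) say the same. In all three schedules the call has a window of plus or minus 3 days.

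The day of the last dose depends on when the first was taken. Section 4.3.2 says of patients who start before 16:00: "For these patients, the tenth dose will be taken in the evening of Day 5". Of those who start later, Appendix 3 says: "For these patients, the 10th dose will be taken on the morning of Day 6".

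**The concern.** One rule follows the patient's dosing and the other follows a telephone call whose date can move by 3 days either way. They agree only when the last dose is on Day 5 and the call is made on Day 33 exactly. In other permitted cases they give different ends to the period over which adverse event incidence, a secondary endpoint, is collected.

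The timing of the call matters because Section 5.3.1 has investigators ask about adverse events at patient contacts, and this call is the last one scheduled. The symptom diary is no substitute: it stops at Day 28, and Section 5.3.5.12 says that adverse event reports are not derived from it. Section 5.6 does not fill the space either, because it applies only after the 28 days and only to serious events thought to be related to study drug. Section 5.3.5.7 ties the recording of deaths to the same period, so its end should be unambiguous.

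**Working it through.** **Inputs**
- Length of the reporting period: 28 days after the final dose (Protocol 5.3.1, 5.4.2.2, 5.6).
- Final dose for patients who complete the twice-daily course: Day 5 evening or Day 6 morning (Section 4.3.2 and the dosing footnotes of Appendices 1–3).
- Closing call: Day 33 ± 3, so Day 30 to Day 36 (Appendices 1–3, column header and footnote d).

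**Formulas**
- End of period = final dose day + 28.
- Days without a scheduled contact = max(0, end of period − call day).
- Days by which the call runs past the period = max(0, call day − end of period).

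**The plan's own figure.** Day 5 + 28 = Day 33, which reproduces the nominal call day. For the later finish, Day 6 + 28 = Day 34, which does not.

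| Final dose | 28-day period ends | Call Day 30 | Call Day 33 | Call Day 36 |
|---|---|---|---|---|
| Day 5 | Day 33 | 3 days short | exact | 3 days beyond |
| Day 6 | Day 34 | 4 days short | 1 day short | 2 days beyond |
| Day 3 (early stop) | Day 31 | 1 day short | 2 days beyond | 5 days beyond |
| Day 1 (only dose) | Day 29 | 1 day beyond | 4 days beyond | 7 days beyond |

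For a Day 5 finish, follow-up after the last dose at the time of the call is 30 − 5 = 25 days, 33 − 5 = 28 days or 36 − 5 = 31 days. For a Day 6 finish it is 24, 27 or 30 days.

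The largest shortfall is 4 of 28 days (4/28 = 14%). It needs both a Day 6 finish and a call on the first permitted day. A Day 5 finisher called at the earliest date is 3 of 28 days short (11%). The documents do not say how often either condition occurs, so an average shortfall cannot be computed.

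For a patient whose only dose was on Day 1, the appendix rule runs past the 28-day rule by 30 − 29 = 1 day to 36 − 29 = 7 days.

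**The case against.** The strongest reply is that the nominal design is coherent. The call is set on Day 33 because that is 28 days after a Day 5 finish, and the footnotes can be read as the practical form of the 28-day rule with an ordinary visit tolerance. That stands for a Day 5 finisher called on time. It does not cover a Day 6 finisher, for whom the on-time call is already 1 day early, or any completer called at the start of the window.

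A reader might infer that the last 3 or 4 days are not covered at all. The documents do not support that. Under Section 5.3.1 the duty to report lasts the full 28 days and includes events that the patient volunteers. Unscheduled visits are allowed, and Section 5.5.1 has known events followed to resolution or stability. What is missing is a scheduled prompt for new events. It remains true that a site working from the appendix footnote alone would take reporting to be closed at the call.

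A reader might also take the longer follow-up of early stoppers as a second defect. Footnote c of each schedule keeps patients who stop drug early in assessments to the end of the study, so the extra days are stated design and not a shortfall.

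Nor do the documents suggest bias between arms. Sites and patients are blinded, and both arms of a cohort share one schedule. SAP Section 5.4.2.2 sets no upper limit on the onset of a treatment-emergent event, and its last onset category is open-ended. The analysis can therefore run without choosing between the two rules, although the rule that a site follows may still decide which late events are recorded.

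**Conclusion.** The inconsistency is in the current text and should be reconciled. For patients who complete the twice-daily course, the last scheduled contact can precede the end of the stated reporting period by up to 3 days (Day 5 finish) or 4 days (Day 6 finish). It does so by 1 day when a Day 6 finisher is called on Day 33.

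This is a minor point. The 14% figure is a compound worst case and describes days without a scheduled contact, not events lost. I assume that late-onset events after a 5-day course are few, in which case the effect on adverse event rates is small; the documents give no rate to test this. The calculation also assumes that the patient stays in the study to the closing call. Sample size, power, alpha and the virology analyses are not affected.

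**What to change.** Reconcile the passages so that one rule defines the end of adverse event reporting in Sections 5.3.1, 5.4.2.2 and 5.6 and in the adverse event footnotes of Appendices 1 to 3.

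Make the window for the closing call forward-only. It should open no earlier than the later of Day 33 and the end of that patient's reporting period: max(33, final dose day + 28). This gives Day 33 for a Day 5 finish and Day 34 for a Day 6 finish. For a Day 1 stopper it gives max(33, 29) = Day 33. The Day 33 floor is needed because a call tied only to the last dose could bring an early stopper's call forward to Day 29, against footnote c.

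Matching edits are needed where the text fixes the end at 33 days: the study duration per patient (Section 3.1), the end-of-study timing (Section 3.2) and the concomitant-medication collection period (Section 4.4 and the appendix footnotes).

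The cost is protocol wording and some calls made later: a call that could now be made on Day 30 would move by at least 3 days, or 4 days after a Day 6 finish.
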